7.8.3 Compliance

Compliance with each PRO questionnaire will be described for each treatment arm, at each time of evaluation, by the number and percentage of expected subjects who filled

out a questionnaire (per subject, at least one question answered) in time of evaluation. The expected number used in calculating the percentage will be all alive subjects who are required to complete the assessment in each treatment arm at each assessment time point except at the first pelvic recurrence time point, which will be the number of alive patients who have the first pelvic recurrence (**Table 42**).

7.8.4 Analyses of PRO

7.8.4.1 Baseline and Change Score Analysis

Descriptive statistics for EORTC QOL-C30, CX24, FSDI and FSDS-R scores (mean, standard deviation) will be presented for each scale and summary scale at baseline for each treatment group (**Table 43**). The change scores from baseline will be generated at each time of post-baseline evaluation and compared between two arms by Wilcoxon test (**Table 44**).

7.8.4.2 Profile Analysis

The profile of change scores over time between two treatment arms will be compared using linear mixed models with the treatment effect, time of assessment from randomization (in months), and their interaction as fixed effects and the intercept and time as two random effects. The estimates for the terms of fixed effect with standard errors and p-values will be presented (**Table 45**).

8. Appendices

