8.0 TREATMENT PLAN

Although the Canadian Cancer Trials Group acts as the coordinating agency for the trial, the responsibility for treatment of patients rests with the individual investigator. Specific details related to trial conduct by each participating GCIG group are included in the Group-Specific Appendix provided by each Group.

After randomization, protocol-assigned surgery must take place within 8 weeks.

Regardless of when the patient is randomized, protocol surgery must be performed within 20 weeks of the date of the initial pathologic diagnosis (NO EXCEPTIONS). A schema of the treatment plan is shown below.

The decision regarding the use of SN lymph node mapping must be made at the time of randomization.

* Regardless of treatment assignment, surgery will include pelvic lymph node dissection with optional sentinel lymph node (SN) mapping. If SN mapping is to be done, the mode is optional, but the laparoscopic approach is preferred.

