The basic hypotheses in QOL and sexual health data analysis are, on average, women managed with simple hysterectomy had lower change scores from baseline on QLQ-CX24 symptom subscale and FSDS-R total score and higher change scores from baseline on FSFI total score relative to women in the radical hysterectomy group. Based on estimates of pooled standard deviations of 13.5, 10 and 21 respectively for change scores on QLQ-CX24 symptom subscale and FSDS-R and FSDS-R total score, we need respectively a total of 120, 130 and 560 women with QOL and sexual health assessments to detect respectively 7, 5, 5 points difference between two treatment arms with 80% power and two-sided 0.05 level in these subscale and scores.

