7.8 Patient Reported Outcomes

The patient report outcomes (PROs) of patients in this study include the quality of life assessed by using EORTC QLQ-C30 (version 3.0) with module QLQ-CX24 and sexual health by the Female Sexual Function Index (FSFI) and the Female Sexual Distress Scale (FSDS-R) before randomization (baseline), at 3 months, 6 months, 12 months, 24 months, 36 months after the surgery but before the first pelvic recurrence, and at the time of the first recurrence. The following are the scoring algorithms for EORTC QLQ-C30, EORTC QLQ-CX24, FSFI and FSDS-R with Q_i denoting the i -th question in the PRO questionnaire.

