3 months	***	** (**)	***	** (**)
6 months	***	** (**)	***	** (**)
12 months	***	** (**)	***	** (**)
24 months	***	** (**)	***	** (**)
36 months	***	** (**)	***	** (**)
At Recurrence	***	** (**)	***	** (**)

Table 43: Summary of Baseline PRO Scale Scores

	Simple Hysterectomy	Radical Hysterectomy	P value*
EORTC QLQ-C30			
Physical Functioning			0.***
N	***	***	
Mean (STD)	**.* (**.*)	**.* (**.*)	
...	
EORTC QLQ-CX.24			
Symptom Experience			0.***
N	***	***	
Mean (STD)	**.* (**.*)	**.* (**.*)	
...	
FSFI			
Desire			0.***
N	**	**	
Mean (STD)	**.* (**.*)	**.* (**.*)	
...	
FSDS-R			
Total Score			0.***
N	***	***	
Mean (STD)	***	***	

* From Wilcoxon test.

Table 44: Summary of Change Scores from Baseline for PRO Scale/Domain/Item at Each Time of Assessment

	Simple Hysterectomy	Radical Hysterectomy	P Value**
Scale/Domain/Item*			
After surgery prior to recurrence			.**
Month 3			
N	***	***	
Mean (STD)	** (**)	** (**)	
Month 6			.**
N	***	***	
Mean (STD)	** (**)	** (**)	
Month 12			.**
N	***	***	
Mean (STD)	** (**)	** (**)	
Month 24			.**
N	***	***	
Mean (STD)	** (**)	** (**)	
Month 36			.**
N	***	***	
Mean (STD)	** (**)	** (**)	
At Recurrence			.**
N	***	***	
Mean (STD)	** (**)	** (**)	

* Table will be provided for each scale/domain/item. ** From Wilcoxon rank sum test

Table 45: Summary of Analysis From Linear Mixed Models for Change Scores

	Estimate	Standard Error	P value
EORTC QLQ-C30			
Physical functioning			
Treatment	**.	**.	0.**
Month	**.	**.	0.**
Treatment*Month	**.	**.	0.**
...			
EORTC QLQ-CX24			
Symptom Experience			
Treatment	**.	**.	0.**
Month	**.	**.	0.**
Treatment*Month	**.	**.	0.**
...			
FSFI			
Desire			
Treatment	**.	**.	0.**
Month	**.	**.	0.**
Treatment*Month	**.	**.	0.**
...			
FSDS-R			
Total Score			
Treatment	**.	**.	0.**
Week	**.	**.	0.**
Treatment*Month	**.	**.	0.**

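### The Treatment row of the PRO mixed model is the fitted arm difference at month 0, before surgery; no row of SAP Table 45 is in general a post-surgery difference, none is named as deciding, and the baseline score is left out

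*SAP*

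**What the plan says.** SAP 7.8 schedules the questionnaires before randomization and then "at 3 months, 6 months, 12 months, 24 months, 36 months after the surgery but before the first pelvic recurrence", with one more at first recurrence.

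Two analyses follow. In SAP 7.8.4.1, "The change scores from baseline will be generated at each time of post-baseline evaluation and compared between two arms by Wilcoxon test"; the Table 44 shell shows N, mean and SD per arm and a p-value at each visit. In SAP 7.8.4.2, the change scores are fitted by "linear mixed models with the treatment effect, time of assessment from randomization (in months), and their interaction as fixed effects", with "the intercept and time as two random effects". Time is therefore a continuous slope, and the baseline score is not a model term. On output: "The estimates for the terms of fixed effect with standard errors and p-values will be presented". Table 45 ("Summary of Analysis From Linear Mixed Models for Change Scores") has rows Treatment, Month and Treatment*Month, and columns for estimate, standard error and p-value. For FSDS-R the time row is printed as Week instead of Month.

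Protocol 14.6 sizes the comparison as one mean difference per scale: 120, 130 and 560 women "to detect respectively 7, 5, 5 points difference between two treatment arms with 80% power and two-sided 0.05 level". On timing, protocol 8.0 says: "After randomization, protocol-assigned surgery must take place within 8 weeks".

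The protocol names the scales and the expected direction (2.5.3 and 14.6) and ranks sexual distress above overall sexual function (2.5.4). Neither document names a visit, a model row or a contrast that decides the comparison.

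**The concern.** A row labelled Treatment in a results table will naturally be read as the effect of the operation. Here it is an extrapolation back to a day when neither arm has been operated on. Depending only on how the arm difference develops after surgery, it can be close to zero or about twice the average difference.

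A constant difference cannot be taken for granted. Protocol 2.2 describes bladder dysfunction in most women straight after radical hysterectomy but long-term dysfunction in 1-2%. Protocol 2.5.2 describes severe dyspareunia in the first 3 postoperative months and severe orgasm problems in the first 6. These are courses within treated women, not arm differences, but they make an early, fading difference plausible.

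With no deciding row, visit or contrast, the choice between the Treatment row, the interaction row and five separate Wilcoxon tests stays open until the data are seen. Leaving out the baseline score also gives up precision that needs no new data to recover.

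**Working it through.** **1. The protocol's own sizes.** Inputs from protocol 14.6: SDs 13.5, 10 and 21; differences 7, 5 and 5; 80% power; two-sided 0.05; 1:1 allocation. The third scale is FSFI, by Table 1 in protocol 2.5.4. Per arm, n = 2(SD/difference)² × (1.960 + 0.842)²:
- QLQ-CX24 symptom scale: 2 × (13.5/7)² × 7.849 = 58.4, total 118
- FSDS-R: 2 × (10/5)² × 7.849 = 62.8, total 126
- FSFI: 2 × (21/5)² × 7.849 = 276.9, total 554

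The t-test version gives 120, 128 and 556, against the stated 120, 130 and 560. So the sizing rests on a single two-sample difference in change score.

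**2. What each row estimates.** The fitted arm difference at month t from randomization is

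D(t) = Treatment + t × (Treatment*Month).

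Hence Treatment = D(0), the day of randomization. Surgery may follow up to 8 weeks later (56/30.4375 = 1.84 months), and the first post-surgery questionnaire is 3 months after that. Treatment equals a post-surgery difference only if the interaction is zero. A reader can compute D(t) for a visit, but its standard error needs the covariance of the two estimates, which Table 45 does not report.

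**3. How far the row can be from the average difference.** The trajectories below are assumed for illustration. Visits are at t = 3, 6, 12, 24, 36 (mean 16.2; sum of squared deviations 748.8). With every visit observed and the covariance in step 4, the expected coefficients are those of a straight line through the five differences. Time is first taken from surgery, that is, with no lag from randomization.
- (a) Growing: 0, 2, 5, 7, 7, mean 4.2. Slope = 151.8/748.8 = 0.203; Treatment = 4.2 − 0.203 × 16.2 = **0.92**. Fitted visits: 1.5, 2.1, 3.3, 5.8, 8.2.
- (b) Fading: 9, 7, 3, 1, 0, mean 4.0. Slope = −195.0/748.8 = −0.260; Treatment = 4.0 + 0.260 × 16.2 = **8.2**. Fitted visits: 7.4, 6.7, 5.1, 2.0, −1.2.
- (c) Constant 7. Slope 0; Treatment = **7.0**.

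The ratio of (b) to (a) is 8.2/0.92, about 9, for nearly equal averages. The line misses the true visit difference by up to 1.7 points in (a) and 2.1 points in (b), both at month 12.

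**4. Power of each row.** Assumptions: 60 per arm and SD 13.5 (protocol 14.6, QLQ-CX24); per-arm covariance 13.5²[ρJ + (1−ρ)I] + s²tt′, with J the all-ones and I the identity matrix, ρ = 0.3, 0.5, 0.7 and s = 0, 0.1, 0.3 points per month; normal approximation, two-sided 0.05, no multiplicity adjustment.

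| Trajectory | Treatment | Treatment*Month | Average over visits |
|---|---|---|---|
| (a) growing | 7% | 59-98% | 44-73% |
| (b) fading | 95-98% | 80-100% | 41-69% |
| (c) constant 7 | 86-93% | 5% | 85-99% |

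There is no general loss of power. The rows simply answer different questions, and which one is significant depends on the shape over time.

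**5. The two clocks.** Visits are dated from surgery and model time from randomization. If all surgery fell 8 weeks after randomization, the same scores would give 0.916 − 0.203 × 1.84 = 0.54 in (a) and 8.219 + 0.260 × 1.84 = 8.70 in (b).

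**6. The baseline score.** With equal variances and baseline/follow-up correlation r, the variance of the baseline-adjusted comparison at one visit, relative to the change score, is (1−r²)/(2(1−r)) = (1+r)/2. For assumed r = 0.3, 0.5, 0.7 this is 0.65, 0.75, 0.85, so the standard error is 19%, 13% or 8% smaller. The documents give no value for r.

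**The case against.** The strongest reply is that Table 45 is not meant to do this job. SAP 7.8.4.2 is a profile analysis, for which the interaction is the natural term. The by-visit comparison is in Table 44, whose N, mean and SD per arm allow an unadjusted difference and an ordinary confidence interval to be worked out at each visit. That is right as far as it goes: the hypotheses are not untested. But Table 44 offers five post-surgery visits per scale, with no deciding visit, no averaged estimate, no stated difference with its interval, and no baseline adjustment.

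Second, a significant interaction would warn the reader. In (a) and (b) it often would. Sixty per arm is the requirement for one scale only; at an assumed 150 per arm the interaction power is at least 93% in (a) and 99% in (b). A warning does not turn the Treatment row into a post-surgery estimate, however.

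Third, the trajectories are invented, and the random slope raises the month-36 SD to √(13.5² + 0.3² × 36²) = 17.3 when s = 0.3. Both are true. The second affects the power ranges, not the coefficients.

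Fourth, the clock shift is small (0.38 and 0.48 points), and omitting the baseline score is not in itself a bias under randomization. Both stand: these are secondary points.

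Fifth, a lighter remedy exists: keep the model and add estimated differences at stated months with intervals. That would mend the reporting but keep the straight-line misfit shown in step 3.

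**Conclusion.** The concern holds. The meaning of the Treatment row follows from the model as written and needs no assumption. So do the absence of a named deciding row or visit and of the baseline covariate. The sizes are illustrative: with assumed average differences of 4.2 and 4.0 points the Treatment row is 0.92 or 8.2, and it equals the post-surgery difference (7.0) when that difference is constant. The trajectories, ρ, s, r and the lag to surgery are all assumed.

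The harm is a misplaced and easily misread coefficient, an open choice of what decides, and avoidable imprecision. The endpoints are secondary and the primary non-inferiority analysis is untouched. The change is recommended, but the main result does not depend on it.

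**What to change.** In SAP 7.8.4.2, replace the straight line with a repeated-measures mixed model: visit as a category (3, 6, 12, 24, 36 months after surgery), treatment, treatment-by-visit and the baseline score as covariate, with the within-patient covariance structure stated. Dating visits from surgery also removes the clock mismatch.

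In Table 45, report the arm difference at each visit with its 95% confidence interval. For the QLQ-CX24 symptom scale, the FSDS-R total and the FSFI total, name in advance one deciding contrast: either the average over visits or one stated visit. Keep the Wilcoxon tests of Table 44 as supportive.

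The cost is SAP wording, one table shell and analysis code; no new data are needed. The model has more parameters. Patients without a baseline score drop out, but change scores already exclude them.

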14.0 STATISTICAL CONSIDERATIONS

14.1 Objectives and Design

The primary objective of this study is to compare the pelvic recurrence rate at 3 years of patients with low-risk cervical cancer defined as lesions less than 2 cm, at least 3mm of intact cervical stroma or with less than 50% stromal invasion and randomized to receive simple hysterectomy and pelvic node dissection or radical hysterectomy and pelvic node dissection. Secondary objectives include comparisons of pelvic relapse-free survival, overall survival, extra pelvic relapse-free survival, rate of sentinel node detection, rate of parametrial, margins and pelvic nodes involvement, treatment-related adverse events, and quality of life (including sexual health). Eligible patients will be randomized in a 1:1 ratio to one of the two treatment arms using the minimization method and the following stratification factors: cooperative group, intended use of SN mapping (yes vs. no); stage (IA2 vs. IB1), histological type (squamous vs. adenocarcinoma, adenosquamous) and tumour grade (1-2 vs. 3 vs. not assessable).

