14.6 Analysis for Quality of Life

The quality of life and sexual health of patients in this study will be assessed by respectively EORTC QLQ-C30 core questionnaire with its module QLQ-CX24, the Female Sexual Function Index (FSFI), and the Female Sexual Distress Scale (FSDS-R). The EORTC QLQ-C30 and QLQ-CX24 are self-administered cancer specific questionnaires with multi-dimensional scales. QLQ-C30 consists of both multi-item scales and single item measures, including five functional domains, a global quality of life domain, three symptom domains, and six single items, while QLQ-CX24 has three multi-item subscales: symptom experience, body Image, and sexual/vaginal functioning, and five single items pertaining to menopausal symptoms, lymphedema, lower back pain, tingling and numbness, and sexual enjoyment. FSFI is a 19-item self-report measure of female sexual function that provides scores on six domains of sexual function (desire, arousal, lubrication, orgasm, satisfaction, and pain) as well as a total score. The FSDS-R is a 13-item unidimensional measure of sexually-related distress. Scoring of the quality of life and sexual health data will be completed following the procedures recommended by the EORTC Study Group on Quality of Life and other published algorithms.

The quality of life and sexual health data will be analyzed to look for statistically and clinically significant differences between two treatment arms. Questionnaire compliance rates will first be ascertained for each group at each measurement time point. Mean scores at baseline and the change scores from baseline at each follow-up assessment time point will be calculated for each subscale and summary scores and compared between two arms by Wilcoxon test. The profile of change scores over time between two treatment arms will be compared using linear mixed models.

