7.5.3 Pelvic Relapse Free Survival (PRFS)

All intention-to-treat patients will be included in the analysis of pelvic relapse-free survival as defined in Section 7.5.1.

A frequency table for the summary of patients with pelvic recurrence, sites of recurrence, censoring and causes of censoring will be provided (**Table 24**). The Kaplan-Meier curve for the PRFS in each treatment arm will be displayed (**Figure 2**).

The hazard ratio of simple hysterectomy to radical hysterectomy with one-sided 95% confidence interval will be computed based on a Cox regression model with a single treated covariate and stratified by the following factors at randomization (**Table 26**):

- Intended use of SN mapping: yes, no
- Histological stage: IA2, IB1
- Histological type: squamous, adenocarcinoma/adenosquamous
- Tumour grade: 1-2, 3, not assessable

Non-inferiority of simple hysterectomy to radical hysterectomy in PRFS will be claimed when the upper limit of the one-sided 95% confidence interval for the hazard ratio of simple hysterectomy to radical hysterectomy is lower than or equal to 2.04, which is corresponding to a margin of 4% for the 3-year pelvic recurrence rate between simple hysterectomy and radical hysterectomy when the 3-year pelvic recurrence rate in radical hysterectomy arm was estimated at 4%. For each level of the baseline factors listed in Section 7.5.2, the 3 year PRFS and the hazard ratio (unstratified) of simple hysterectomy over radical hysterectomy with upper limit of the one-sided 95% C.I. will be presented. A “per-protocol” sensitivity analysis will also be performed (Table 26).

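### The PRO mixed model omits all five minimisation factors; if they predict change scores, the standard errors of its arm contrasts are somewhat conservative (minor)

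*SAP*

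**What the plan says.** Protocol 14.1 allocates women 1:1 "using the minimization method and the following stratification factors: cooperative group, intended use of SN mapping (yes vs. no"), followed by stage, histological type and grade.

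Protocol 14.6 plans the repeated-measures PRO comparison in one sentence and names no covariates: "The profile of change scores over time between two treatment arms will be compared using linear mixed models". SAP 7.8.4.2 fills in the model. The fixed effects are given as "with the treatment effect, time of assessment from randomization (in months), and their interaction as fixed effects". Each woman also has a random intercept and a random slope. SAP Table 45 reports three rows per scale: treatment, time and their product. The per-visit Wilcoxon tests in SAP 7.8.4.1 are also unadjusted.

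The SAP treats its survival-type secondary endpoints differently. In 7.5.3 the Cox model is "stratified by the following factors at randomization", listing SN mapping, stage, histology and grade but not cooperative group. Sections 7.5.4 to 7.5.6 carry the same four factors into the log-rank tests and Cox models. No reason is given for using none of them in the PRO model.

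**The concern.** Minimisation balances the arms on its factors. If those factors also predict the outcome, the treatment estimate varies less from trial to trial than it would under simple randomisation. A linear model that leaves the factors out still counts their variance as error, so its standard error is larger than the true sampling error and its p-values are too large.

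The PRO comparison carries the hypotheses that simple hysterectomy does less harm to pelvic symptoms, sexual distress and sexual function (Protocol 2.5.3). Those hypotheses are about average differences in change, so the arm contrast matters. The PRO analysis should also have far more data to support covariates than the recurrence analyses: SAP 2.1 records only 14 pelvic recurrences two years after accrual ended.

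**Working it through.** **Inputs.** Standard deviations and target differences come from Protocol 14.6: "Based on estimates of pooled standard deviations of 13.5, 10 and 21 respectively for change scores", with differences of 7, 5 and 5 points, 80% power and two-sided 0.05. The third score is FSFI according to Table 1 in Protocol 2.5.4. The share of change-score variance explained by the five factors, R², is not in the documents. It is assumed here over 0 to 0.30.

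**1. The plan's own sample sizes.** With n per arm = 2(SD/δ)²(1.960 + 0.842)², rounded up:
- QLQ-CX24 symptom scale: 2(13.5/7)² × 7.85 = 58.4, so 59 per arm and 118 in total (plan: 120).
- FSDS-R: 2(10/5)² × 7.85 = 62.8, so 63 per arm and 126 in total (plan: 130).
- FSFI: 2(21/5)² × 7.85 = 276.9, so 277 per arm and 554 in total (plan: 560).

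The t-test version gives 120, 128 and 556. The plan's sizes therefore reproduce with unadjusted SDs, and the planned 80% power does not rely on covariates.

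**2. Standard error of a between-arm mean difference.** The ratio of unadjusted to adjusted SE is 1/√(1 − R²):

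| R² | 0 | 0.02 | 0.05 | 0.10 | 0.20 | 0.30 |
|---|---|---|---|---|---|---|
| SE ratio | 1.000 | 1.010 | 1.026 | 1.054 | 1.118 | 1.195 |

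**3. Which terms of the specified model are affected.** Generalised least squares standard errors were computed for the SAP model at months 3, 6, 12, 24 and 36. The assumed variance was 60% random intercept and 30% residual, with a small slope variance. Here R² is the share of the intercept variance explained. SE ratios with complete data:

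| R² | Arm at month 0 | Arm at month 15 | Arm-by-time |
|---|---|---|---|
| 0.05 | 1.020 | 1.022 | 1.000 |
| 0.10 | 1.042 | 1.045 | 1.000 |
| 0.20 | 1.089 | 1.097 | 1.000 |

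With an assumed dropout pattern the arm-by-time ratio was at most 1.001, at R² = 0.30. The reason is that with complete data the variance of the slope difference depends only on slope variance and residual variance. Factors that shift a woman's overall level do not enter it.

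**4. Error rates.** Minimisation on five factors was simulated for a single change score: 560 women, 1,500 runs per R², assumed factor prevalences, assignment probability 0.9.

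| R² | Unadjusted: mean SE / true SD | Type I error | Adjusted: mean SE / true SD | Type I error |
|---|---|---|---|---|
| 0 | 0.0845 / 0.0854 | 5.3% | 0.0845 / 0.0855 | 5.2% |
| 0.05 | 0.0845 / 0.0841 | 5.3% | 0.0824 / 0.0840 | 5.9% |
| 0.10 | 0.0845 / 0.0787 | 3.5% | 0.0802 / 0.0786 | 4.7% |
| 0.20 | 0.0846 / 0.0745 | 3.0% | 0.0757 / 0.0741 | 4.9% |

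The Monte Carlo standard error of a 5% rate is √(0.05 × 0.95/1,500) = 0.6 points, so the rows at R² of 0.05 or less show no clear departure from nominal. A separate simulation with 400 women, nine groups and assignment probability 0.8 gave 3.9% unadjusted and 4.9% adjusted at R² = 0.10, and 3.0% and 4.9% at 0.20. The true spread of the estimate is the same with or without adjustment. Only the reported SE and p-value differ.

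**5. Power.** With SE = 2 × SD/√N and power = Φ(δ/SE − 1.96), at an illustrative N = 400:
- QLQ-CX24: SE = 1.35, power Φ(3.23) = 99.9% unadjusted.
- FSDS-R: SE = 1.00, power Φ(3.04) = 99.9% unadjusted.
- FSFI: SE = 2.10, power Φ(0.42) = 66% unadjusted. At R² = 0.10 the SE is 1.99 and power is Φ(0.55) = 71%.

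At the plan's 560 women, FSFI power is 80.4% unadjusted, and 82.4%, 84.4% and 88.3% at R² of 0.05, 0.10 and 0.20.

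Four hundred is not arbitrary for FSFI. Women reporting no sexual activity skip the later items, and the half-items rule in SAP 7.8.1.4 would then leave the total missing if skipped items count as missing. Protocol 2.5.2 cites 43.3% not sexually active in a long-term cohort. If that applied here, 700 × 0.567 ≈ 397 women would have a total.

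**6. Cost if the factors do not matter.** At R² = 0 the adjusted SE was about 0.2% larger at 400 women and about 2% larger at 120. In simulation at 120 women with a 7-point effect, adjustment moved power from 79% to 77% at R² = 0, and from 82% to 84% at R² = 0.10.

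**The case against.** The strongest objection is that the documents do not show these factors predicting change scores. Stable differences between groups or languages are largely removed by subtracting baseline. Adjuvant radiation, which Protocol 2.5.1 links to worse scores, is not a minimisation factor, and Protocol 5.2.6 excludes women for whom it is already planned. The lymphoedema reduction with sentinel mapping quoted in Protocol 2.3 is from vulvar cancer. Here both arms include pelvic node dissection, and SAP 7.8.1.2 scores lymphoedema outside the symptom scale. Nothing is offered for stage, histology or grade. All of this stands, so R² could be close to zero and the effect must be stated conditionally.

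A reader might infer that the planned standard errors are known to be too large, that the treatment-by-time comparison is weakened, or that planned power is lost. The documents support none of these. The first needs an R² they do not give. The second fails because main effects leave that standard error essentially unchanged. The third fails because the sample sizes already use unadjusted SDs. Nor is a true difference on QLQ-CX24 or FSDS-R likely to be missed at 400 women. Whether the mixed model or the Wilcoxon tests should lead is a separate choice that does not follow from the omitted factors.

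Balance is also uncertain in the set analysed. SAP 7.8.2 restricts it to treated women with at least one questionnaire, and the sexual health component is optional (Protocol 6.0). The simulated error rates therefore cannot be asserted for FSDS-R or FSFI. The same fact favours adjustment, which protects against any imbalance that selection into the subset creates.

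**Conclusion.** The omission is plain in SAP 7.8.4.2 and Table 45, and it is at odds with the SAP's handling of its survival-type secondary endpoints. The consequence is avoidable imprecision: the unadjusted test is valid to conservative. The affected quantities are the arm term and average or visit-specific arm contrasts, with an SE overstated by about 1% to 3% at R² of 2% to 5%, 5% at 10%, 12% at 20%, and not at all at zero. These figures assume that minimisation balance holds in the PRO set, and they come from the formula for a single mean difference. The mixed-model ratios are slightly smaller under the assumed variance split. FSFI is the only one of the three scores where the gain could matter in practice. The point is minor.

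**What to change.** In SAP 7.8.4.2, add intended use of SN mapping, stage, histological type, grade and cooperative group, as recorded at randomization, as fixed effects. Pool cooperative groups that contribute few PRO participants. Report the arm contrast from that model, averaged over visits or at each visit. With time measured from randomization and an interaction in the model, the treatment coefficient alone is the arm difference at month zero, so Table 45 needs a row for the contrast. If the sponsor prefers the unadjusted model, a sentence justifying the omission would do.

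The change is one sentence in the SAP and a few terms in the model statement. SAP 7.1 already takes the stratification factors from the Centralized Randomization File. The statistical cost is at most 13 degrees of freedom (8 for nine groups, 1 each for mapping, stage and histology, 2 for grade), fewer after pooling.
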